## e) Study Endpoints

**Primary Outcome:** Development of SSI within study follow-up period. **Secondary Outcomes:** Length of hospital stay and serious adverse events.

## f) Procedures Involved in the Human Research

Subjects will be consented prior to each eligible surgery. Prior to surgery, each prospective subject will be interviewed by a member of the study team and a medical history will be obtained. Randomization will occur prior to the start of surgery. The subject will then undergo their scheduled surgery and if they are placed in the experimental arm, they will receive the negative pressure wound therapy. If the subject is in the control arm, they will receive the standard of care wound dressings. Post-operatively, each patient will be followed for up to 37 days and monitored for the development of an SSI and secondary outcomes. If there is no evidence of a wound infection by post-operative day 5, the NPWT device will be removed. A follow-up, outpatient assessment at 30 days ( $\pm$  7 days) post-operatively will be included for all patients who did not develop a SSI.

It is anticipated that approximately 2% or less of subjects enrolled into this study will require re-operation of the principal incision for within 5-7 days after the original surgery due to various life-threatening complications which may include bleeding, anastomotic dehiscence or other septic complications. For subjects requiring re-

	Protocol Title:	Prophylactic Negative Pressure Wound Therapy to Reduce Surgical Site Infections in Elective Clean-Contaminated Colon Resections
	Principal Investigator	[name]
	Name/Contact Info:	[name], [contact]
Mount	Primary Contact	[name]
Sinai	Name/Contact Info	[name], [contact]
	Date Revised:	10/10/2018
	Study Number:	

intervention, who did not develop an SSI prior to the reoperation, the NPWT device will be re-applied and the study period re-defined based on the latter procedure.

	Screening ≤ 30 days preop	Baseline	Day 1	Day 2	Day 3	Day 4	Day 5	Final Visit 23 to 37 days post op
Study Activity								
Informed Consent	X							
Enrollment Criteria	Х							
Demographic/ Clincal Information		X						
Medical History	Х							
Inclusion/Exclusion Criteria	Х							
Randomization		Х						
Surgery		Х						
Application of NPWT Device		Х						
Bloodwork	Х			X*			X*	
SSI Assessment		Х	Х	Х	Х	X	Х	Х
AE Monitoring	Х	Х	Х	Х	Х	Х	Х	Х
Concomitant Medications	Х	Х	Х	Х	Х	Х	Х	Х

Study schedule of events. \* indicates that study event may occur with 24 hours of study visit.

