### 2) Background

Surgical site infections (SSIs) are a common cause of nosocomial infections, and a major contributor to patient morbidity, mortality and unnecessary healthcare costs

	Protocol Title:	Prophylactic Negative Pressure Wound Therapy to Reduce Surgical Site Infections in Elective Clean-Contaminated Colon Resections
	Principal Investigator Name/Contact Info:	[name] [name], [contact]
Mount	Primary Contact	[name]
Sinai	Name/Contact Info	[name], [contact]
	Date Revised:	10/10/2018
	Study Number:	

(1,2). The overall SSI rate in elective, clean-contaminated colon resections has been reported as high as 25%, the highest SSI rate among all elective surgical procedures (1). There has been a national trend in instituting pre-operative and post-operative measures to prevent SSIs (colon bundle), which was found to reduce the relative SSI rate by over 50% (3). At the Mount Sinai Hospital, the colon bundle protocol includes bowel decontamination by mechanical preparation and/or oral antibiotics, monitoring and maintenance of a normal perioperative glycemic index, hair clipping outside the OR, a preoperative chlorhexidine wash, a wound protector, intravenous antibiotics, a separate closing tray, and changing of sterile scrubs prior to closing. The colon bundle was first instituted in 2014 at Mount Sinai, and despite these efforts, while the overall SSI rate has declined, for high-risk, clean-contaminated cases in patients with inflammatory bowel diseases (IBD) or who are undergoing re-operative bowel surgery, the SSI rate remains at around 25%.

Negative pressure incision wound therapy represents a possible opportunity to reduce SSIs in colorectal surgery even further. This technology was initially studied in orthopedics and later in trauma surgery. In colorectal surgery, a retrospective study assessed the use of negative pressure incision wound therapy applied in clean-contaminated cases, compared to standard of care, and found a greater than 50% reduction in the SSI rate (4). However, the intraoperative use of NPWT applied immediately following skin closure has not yet been determined in a prospective, randomized fashion to reduce SSI in clean-contaminated colon resection cases (5).

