## b) Inclusion and Exclusion Criteria

All patients from aged 18 or older who will undergo an open or laparoscopicassisted clean-contaminated or contaminated colorectal surgical procedure will be included if they meet the following criteria. Patients must either have an inflammatory bowel disease, undergoing a stoma reversal, undergoing reoperation within 30 days, or have two or more of the following risk factors: presence of an ostomy, creation of an ostomy, type II diabetes, BMI greater than 30, immunosuppression, malnutrition, current smoker, chronic kidney disease (creatinine > 1.2), and disseminated cancer. Exclusions include patients currently enrolled in another interventional clinical trial, patients with a current infection (including a known urinary tract infection), patients allergic to or hypersensitive to silver, patients planning to undergo a second colorectal surgical procedure (e.g., colostomy or ileostomy takedown) or any other general surgery in less than 30 days of index-surgery, any patient in which the planned surgery would include: i) placement of a stoma in the principal incision; ii) placement of a drain into the supra-peritoneal fascia space that emerges through the principal incision; iv) placement of a drain into the intraperitoneal space that emerges through the principal incision; and v) supplementation of any of the irrigation fluid with antibiotic or antiseptic drugs, patients with healing disorders, pregnant women, prisoners, or any patient that is deemed unsuitable for the study by the Principal Investigator or the operating surgeon/Co-Investigator.

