## c) Number of Subjects

Up to 400 subjects are expected to be consented at this site. A series of 330 high risk patients undergoing elective, open or laparoscopic-assisted, clean contaminated cases involving colon resection will be enrolled in this study, of which 110 patients will receive an intraoperative application of NPWT and 220 control patients will receive the standard of care. This number was chosen based on a power analysis. Assuming the NPWT group will have a 50% reduction from the current clean-contaminated colon resection SSI rate of approximately 25%, a two-sided, chi-square power analysis indicated that with a 2:1, control to experimental ratio, 330 total subjects will be needed to detect this difference with 80% power. This number was rounded up to a

	Protocol Title:	Prophylactic Negative Pressure Wound Therapy to Reduce Surgical Site Infections in Elective Clean-Contaminated Colon Resections
	Principal Investigator	[name]
	Name/Contact Info:	[name], [contact]
Mount	Primary Contact	[name]
Sinai	Name/Contact Info	[name], [contact]
	Date Revised:	10/10/2018
	Study Number:	

total of 400 patients expected to be consented in order to account for screen failures, changes in operative and post-operative treatments, and subjects lost to follow-up. These patients will be allocated to each study arm using a simple randomization scheme. Mount Sinai performed almost 1,000 clean-contaminated colon resections in 2015, and we believe the proposed study can be completed in less than 2 years from the first enrollment.

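### The arm is assigned before surgery, with no concealment described, although it decides only the dressing put on at the end of the operation

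*Combined protocol and SAP*

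**What the plan says.** Section 5f fixes the order of events: "Randomization will occur prior to the start of surgery". The patient then has the scheduled operation and receives the device if in the experimental arm; otherwise, "If the subject is in the control arm, they will receive the standard of care wound dressings". The schedule of events lists randomisation, surgery and device application together under Baseline.

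The documents put the device at the end of the operation in slightly different words. The Brief Summary speaks of the immediate postoperative period and section 5c of an intraoperative application. The Background (section 2), describing the evidence gap, refers to "the intraoperative use of NPWT applied immediately following skin closure". Section 5f itself does not mention closure.

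On allocation, section 5c says only that patients are "allocated to each study arm using a simple randomization scheme". No section describes concealment, blinding of the operating team or delayed release of the assignment.

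Two passages limit how far operative care could vary. The hospital's colon bundle (section 2) includes "a wound protector, intravenous antibiotics, a separate closing tray, and changing of sterile scrubs prior to closing". Section 5b excludes "any patient in which the planned surgery would include" certain stomas or drains in the principal incision, or "supplementation of any of the irrigation fluid with antibiotic or antiseptic drugs".

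**The concern.** Nothing before closure depends on the arm, yet the assignment exists throughout the operation. That is the period in which the wound may be contaminated and is closed, and the primary outcome (section 5e) is SSI. A team that knows the arm could, without intending to, handle the wound differently. The resulting difference in SSI would be counted as an effect of the device, or would hide one.

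Analysing every patient as randomised does not help, because the difference arises after assignment and stays in the comparison. What removes this route is that the team does not know the arm until the wound is closed.

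The bundle and the exclusions narrow the room for this but do not close it. The exclusions apply to the surgery as planned, so an unplanned drain or an irrigation choice made during the case remains a matter of judgement.

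**Working it through.** **The plan's own figure.** The plan gives no figure on this point. Its arm sizes (220 control, 110 NPWT) and event rates (25% and 12.5%) come from section 5c. Alpha is not stated; 0.05 two-sided is assumed. With mean proportion (220 × 0.25 + 110 × 0.125)/330 = 0.2083, the standard error is 0.0474 under the null and 0.0430 under the alternative. Power is Φ((0.125 − 1.96 × 0.0474)/0.0430) = 77.2% (77.7% by exact enumeration), against the stated 80%. That shortfall is a separate matter. The time of randomisation does not enter the sample-size formula.

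**Illustration of bias.** Let x of 220 control and y of 110 NPWT patients have an SSI, and let p = (x + y)/330. The test statistic is z = (x/220 − y/110)/√[p(1 − p)(1/220 + 1/110)], significant if |z| > 1.96. The probability of a significant result is the sum of Bin(x; 220, control rate) × Bin(y; 110, NPWT rate) over all significant pairs (x, y). The device is assumed to have no effect, so any difference between the rates comes from operative care alone. The shifts of 1 to 3 points are assumptions; the documents give none.

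| Control SSI | NPWT SSI | Any significant result | Significant, favouring NPWT |
|---|---|---|---|
| 25% | 25% | 5.0% | 2.3% |
| 25% | 24% | 5.3% | 3.6% |
| 25% | 23% | 6.5% | 5.5% |
| 25% | 22% | 8.7% | 8.2% |
| 24% | 25% | 5.6% | 1.4% |
| 23% | 25% | 7.1% | 0.9% |
| 22% | 25% | 9.8% | 0.5% |

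The shifts are small against the sampling error: √[0.25 × 0.75 × (1/220 + 1/110)] = 0.0506, so 3 points is 0.03/0.0506 = 0.59 standard errors.

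**How large a shift is reachable.** Three points averaged over an arm is 3/25 = 12% of all its SSIs. Suppose the route is unplanned drains or stomas, in an assumed 2% to 5% of cases at an assumed 40% SSI risk. Preventing every SSI in those cases moves the arm by only 0.02 × 40 = 0.8 to 0.05 × 40 = 2.0 points. A larger shift needs something that touches more patients, such as irrigation or closure technique.

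**Exclusion after randomisation.** Dropping 5% of the NPWT arm at 40% risk leaves a rate of (0.25 − 0.05 × 0.40)/0.95 = 24.2% and a false-positive rate of 5.1%. Dropping 2% leaves (0.25 − 0.02 × 0.40)/0.98 = 24.7% and 5.0%. Both are close to the 5.0% with no exclusion.

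**The case against.** The strongest reply is that the harm depends on three steps: the team learns the arm, operates differently, and thereby changes SSI. The documents establish none of these. Silence on concealment may be only a gap in reporting. An assignment generated before surgery and sealed until closure would satisfy section 5f as written. The bundle already standardises several steps, and no document suggests that irrigation or closure would vary by arm. All of this stands. It sets the strength of the point (the team may know) and shows that the essential change is non-disclosure rather than the moment at which the assignment is generated.

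Three stronger readings are tempting, and the documents do not support them.

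- *The result will be biased towards NPWT.* The direction is unknown. A surgeon who knows that a patient is a control might take extra care, and the lower rows of the table then apply.
- *Operative changes after randomisation are a material source of bias.* The enlargement to "400 patients expected to be consented in order to account for screen failures, changes in operative and post-operative treatments" counts from consent, so some of those changes may come before randomisation. Section 5c states no exclusion rule, and section 5f keeps patients who need re-operation. The calculated effect is also negligible.
- *Eligibility should be re-checked against the operation actually performed.* That would replace the planned-surgery population of section 5b with one defined by events in the operating room. It would also require more patients to reach closure: 337, 348 or 367 to randomise 330 if an assumed 2%, 5% or 10% failed. It is a debatable trade-off and is not needed to close the route described here.

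**Conclusion.** The point holds as a risk that the plan leaves open, not as a demonstrated bias. Assignment before surgery is explicit, the arm is not needed until the dressing is applied, and no section keeps it from the operating team. That application follows skin closure is a reasonable inference from several sections; section 5f does not state it.

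The size cannot be determined from the documents. Under the stated assumptions, a 1-point shift barely matters (5.3% or 5.6% against 5.0%). A 3-point shift would raise the false-positive rate to 8.7% if it favoured NPWT. If it favoured control, false results for NPWT would fall to 0.5%, while significant results of either sign would rise to 9.8%. The larger shifts are hard to reach through unplanned drains and stomas alone. This is a cheap improvement of low to moderate severity, held with medium confidence.

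**What to change.** In section 5f, replace "Randomization will occur prior to the start of surgery" with:

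> Eligibility is confirmed before surgery under 5b as written. The assignment is generated, or a concealed assignment is opened, only when skin closure is complete and before any dressing is applied; the operating team does not know the arm before then.

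Leave the planned-surgery exclusions in 5b unchanged and add no re-check against the operation performed.

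**Cost.** Existing staff open a sealed or web-based assignment in the operating room. A device must be on hand for every case, about 330 rather than 110, although section 19 stores the devices in a locked office; the number used does not change. The target sample size is unaffected.

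**What it does not do.** The dressing is still visible at the SSI assessments on days 1 to 5, so assessment and care after surgery remain unmasked. For the roughly 2% or fewer expected to need early re-operation, the arm will already be known at the second operation.

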### Brief Summary of Research (250-400 words):

The purpose of this study is to see if the Negative Pressure Wound Therapy (NPWT) system is effective and safe for the prevention of superficial and deep incisional surgical site infections (SSI) in high risk patients within 30 days after elective colorectal surgery. It has been shown that patients with an IBD, patients undergoing a reoperation or patients with certain comorbidities are at a higher risk of developing an SSI. The NPWT device is a wound dressing with a vacuum system that can be placed over abdominal wounds. The study will include up to 400 patients at this single site, where these high risk patients will be randomized to receive either one of two arms. The first arm involves the placement of the NPWT device in the immediate postoperative period over abdominal wounds after clean-contaminated and contaminated colorectal surgical procedures. The device would then be left on for 5 days. The second arm would be standard of care and would entail routine postoperative protocols. Subjects will then be seen once at a 30 day ( $\pm$  7 days) follow-up visit to assess for the development of SSIs.

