### 1) Objectives:

Research Question: Does the application of the NPWT device immediately after surgery work and is it safe for the prevention of superficial and deep incisional surgical site infections (SSI) in high risk patients within 30 days after elective colorectal surgery when compared to standard of care of the same population?

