### 4) Resources Available to Conduct the Human Research

There are multiple investigators involved in this study in addition to the Principal Investigator, [name] M.D. The Principal Investigator and Co-Investigators all have extensive experience conducting research at the Mount Sinai Medical Center. Additionally, a research coordinator is employed and will be involved in the consent and data collection processes. Prior to participation, each of the investigators will have read the protocol and understand what it involves and what each of their specific responsibilities entail. The recruitment goal for this study is about 400 patients in 24 months. The investigators conduct about 83 clean/contaminated bowel resections each month. In order to meet the recruitment goal, between 15 and 20 patients would need to be consented each month. Because the vast majority of the study data-points are derived from the standard of care perioperative assessments, intraoperative clinical documentation, and the standard of care follow-up visits, meeting this screening and enrollment goal is feasible.

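### SSI has no stated criteria, assessor or masking, and on days 1 to 4 it is to be assessed with the device over the incision in the NPWT arm, so ascertainment could differ between arms

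*Combined protocol and SAP*

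**What the plan says.** The combined protocol and SAP gives the primary outcome in section 5e as "Development of SSI within study follow-up period". Section 1 is narrower. It speaks of "prevention of superficial and deep incisional surgical site infections (SSI) in high risk patients within 30 days after elective colorectal surgery", which names two depths and a 30-day window but gives no diagnostic criteria.

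Section 5f says that "each patient will be followed for up to 37 days and monitored for the development of an SSI and secondary outcomes". It does not say who decides that an SSI is present, whether that person knows the arm, or whether calls are adjudicated. No other section does so either.

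On cover of the incision:

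- NPWT arm: the Brief Summary says "The device would then be left on for 5 days". Section 5f adds "If there is no evidence of a wound infection by post-operative day 5, the NPWT device will be removed".
- Control arm: section 5f says "they will receive the standard of care wound dressings". The type of dressing, its wear time and its change schedule are not stated.

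The schedule in section 5f has one row, "SSI Assessment", for both arms. It is marked at baseline, on each of days 1 to 5, and at the final visit (days 23 to 37). The text of section 5f provides the 30-day assessment for patients who have not had an SSI. The schedule row does not repeat that limit.

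**The concern.** Superficial incisional SSI is partly a matter of judgement. Here the judgement is made without written criteria by an unnamed assessor, and no masking is described. The protocol does not use the term open-label, but a visible device compared with ordinary dressings makes it a safe inference that anyone examining the wound in the first days will know the arm.

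Two features could make recording differ between arms. First, on days 1 to 4 the NPWT incision lies under the device, and the plan does not say how SSI is then to be assessed. Second, a positive call made in those days is not rechecked at day 30. If control incisions are seen more often, passing redness could be called SSI and stay on record, while the same redness under a device could settle unseen.

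At stake is whether a difference in SSI rates reflects the treatment or the way SSI was looked for. The interim look in section 5d, which may change enrolment, would inherit the same error.

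**Working it through.** **Inputs.** From section 5c: 110 NPWT and 220 control patients; control SSI rate 25%; a 50% reduction, so 12.5% on NPWT; two-sided chi-square test; 80% power. Alpha is not stated; 0.05 is assumed. The 20% rate used below is an assumed lower alternative.

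**The plan's own figure.** With k = 2 controls per NPWT patient and p̄ = (0.125 + 0.25)/2 = 0.1875:

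n(NPWT) = [1.960·√(p̄(1−p̄)(1+1/k)) + 0.842·√(p₁(1−p₁) + p₂(1−p₂)/k)]² / (p₂−p₁)²

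= [1.960·√0.2285 + 0.842·√0.2031]² / 0.015625 = 110.9, so 111.

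The total is 3 × 111 = 333, against the stated 330. The figure is reproduced to within 1%. (With p̄ weighted by allocation the total is 354.) The sample size is not at issue here; it supplies the arm sizes for what follows.

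**How much the cover alone could lose.** Let m be the share of NPWT-arm SSIs never recorded. Then

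m = (share of SSIs arising on days 1 to 4) × (share of those never recorded at day 5 or later).

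The documents give neither factor. For example, 20% × 25% = 5%, and 40% × 50% = 20%. If every hidden case is recorded later, m = 0.

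**Effect on false positives.** Take a true SSI rate p in both arms, so there is no treatment effect. The recorded NPWT rate is p(1−m) and the recorded control rate is p. The rejection probability of the uncorrected chi-square test was summed exactly over the two binomial distributions (110 and 220), counting only results that favour NPWT.

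| m (assumed) | recorded NPWT rate, p = 20% | chance favouring NPWT | recorded NPWT rate, p = 25% | chance favouring NPWT |
|---|---|---|---|---|
| 0 | 20.0% | 2.3% | 25.0% | 2.3% |
| 5% | 19.0% | 3.7% | 23.75% | 4.1% |
| 10% | 18.0% | 5.8% | 22.5% | 6.7% |
| 20% | 16.0% | 13.0% | 20.0% | 16.4% |

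**False early calls in controls.** Suppose instead that 5% of SSI-free controls, and no NPWT patients, are wrongly called. The recorded control rate is 0.20 + 0.80 × 0.05 = 24.0%, or 0.25 + 0.75 × 0.05 = 28.75%. The chance of a significant result favouring NPWT is then 11.9% or 10.2%. The 5% is an assumption.

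**The opposite direction.** Section 6 lists redness and irritation of the wound as a possible effect of the device. Take the planned true effect (12.5% against 25%) and suppose that a share f of SSI-free NPWT patients is wrongly called SSI. The recorded NPWT rate is 0.125 + 0.875f, and exact power is:

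| f (assumed) | recorded NPWT rate | power |
|---|---|---|
| 0 | 12.5% | 77.7% |
| 2% | 14.25% | 62.5% |
| 5% | 16.875% | 38.3% |

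**The case against.** A reader might infer more: that control wounds are inspected daily while NPWT wounds are hidden, that the treating team makes the call, and that detection therefore differs in favour of NPWT. The documents do not support that.

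- **Cover.** Control incisions are dressed too. Their change schedule is not given, so more frequent inspection of controls is an assumption. What stands is that the device has a stated 5-day wear time, no equivalent is stated for control dressings, and nothing in the plan makes inspection equal.
- **Delay rather than loss.** The outcome accumulates to day 37, both arms are assessed at day 5 and at the final visit, and removal of the device is itself tied to a check for infection. Cover on days 1 to 4 therefore mainly delays detection. A true case is lost only if it resolves, or is treated without being recorded, before the incision is seen. This is a strong answer for missed cases. It does not answer false early calls, which later visits as planned would not correct.
- **Finality.** The rule that ends assessment after an SSI applies to both arms, so it is not biased in itself. It matters only if early calls are more frequent in one arm.
- **Assessor.** No section assigns the call to the treating team. The gap is that nobody is named.
- **Direction.** Device-related redness could be over-called as SSI, which would work against NPWT.
- **Feasibility.** Section 3 spreads follow-up over the medical center and affiliated practices, and section 5b treats the operating surgeon and the co-investigator as one role. A masked, non-operating assessor at every visit is not shown to be available. That limits the remedy, and the fix below allows for it.

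**Conclusion.** The point holds as a design weakness that should be corrected. The primary outcome has no stated criteria, assessor or masking; the method of assessment under the device on days 1 to 4 is not described; and an early positive call is not rechecked. Differential ascertainment is therefore possible.

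It plausibly favours NPWT, but neither direction nor size can be determined from the documents. Every inflated error rate above rests on an assumed share of lost or false calls, and on an assumed alpha of 0.05. The range includes no bias at all, with the chance favouring NPWT staying at 2.3%, if hidden cases are recorded at day 5 or later. The finding is not that the trial will show a false benefit. It is that the plan does not guard against error in either direction, although visits already scheduled would allow it to.

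**What to change.** 1. Name one standard set of criteria for superficial and deep incisional SSI, and apply it in both arms.
2. Make the outcome determination at common times with the incision uncovered in both arms: at day 5 and at the day 23 to 37 visit. Include patients with an earlier SSI call at both. This concerns when the outcome is determined, not how long the device or dressing is worn. Section 5f does not say what happens to the device if infection is suspected at day 5; the investigators should state how the determination is made in that case.
3. Where existing staffing allows, have the determination made by a co-investigator who did not operate and is not told the arm. Section 4 says "There are multiple investigators involved in this study in addition to the Principal Investigator", so this may be possible without new staff for at least part of the visits.
4. Pre-specify a sensitivity analysis that counts only SSIs present at or after day 5 in both arms. Report it beside the primary analysis of all SSIs, not in its place, because it may drop true early SSIs that had resolved by then.

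The cost is protocol wording, one further analysis and some scheduling. The final visit for patients with an earlier SSI adds little, because section 4 describes follow-up visits as standard of care. Masking will be imperfect, particularly at day 5, when the device has only just come off.

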## 3) Setting of the Human Research

Informed consent will be obtained in the offices of one of the investigators while the patient is in for an office visit or at the Mount Sinai Pre-Surgical Testing Center before the patient's screening visit. No study related tests will be performed prior to informed consent. The screening visit and surgery will take place at Mount Sinai Medical Center. The follow-up visits will take place at either the Mount Sinai Medical Center or at Mount Sinai-affiliated off-site practices. Statistical analyses will be performed on de-identified data at Mount Sinai in collaboration with the Department of Biostatistics.

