### d) Study Timelines

Subjects will be contacted and consented prior to surgery, and will then be followed for up to 37 days after the surgery. It is anticipated that subjects will be enrolled through June 2020. The study should be closed out between September 2020 and September 2021. An interim analysis will be conducted when approximately 50% of the subjects have completed 30 day follow-up (55 treatment; 110 control). This will allow the assumptions used to plan the study to be verified or it will allow the planned study enrollment to be adjusted.

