#### **MSSM Principal Monitor:**

Principle Investigator:

First Name: [name] Last Name: [name] Academic Title: Clinical [name]: Surgery Mailing Address: [name] [contact] [contact] E-mail: [contact]

2. Justify your choice of principal monitor in terms of the assessed risk to the research subject's health and wellbeing. In high risk studies when the principal monitor is independent of the study staff, indicate the individual's credentials, relationship to the PI, and the rationale for selection. [name] is the PI of the study and

	Protocol Title:	Prophylactic Negative Pressure Wound Therapy to Reduce Surgical Site Infections in Elective Clean-Contaminated Colon Resections
	Principal Investigator Name/Contact Info:	[name] [name], [contact]
Mount Sinai	Primary Contact Name/Contact Info	[name] [name], [contact]
	Date Revised:	10/10/2018
	Study Number:	

designated principal monitor. He is a certified, accomplished colorectal surgeon with extensive clinical and research experience on colorectal operations and wound management.

3. List the specific items that will be monitored for safety: Adverse events

4. Indicate the frequency at which **ACCUMULATED** safety and data information: At least annually—more often depending on volume of enrollment.

6. Where applicable, indicate dose selection procedures that will be used to minimize toxicity: This is a phase 3 trial, so dosing ranges to minimize toxicity have already been established.

7. List any specialized grading system that will be used to evaluate adverse events: N/A

 8. Describe procedures that will be used to assure data accuracy and completeness: Periodic monitoring visits where the monitor will go through collected data, confirming with source documents the accuracy and completeness of the data.
9. Should a temporary or permanent suspension of your study occur, in addition to the PPHS, indicate to whom (NIH, FDA, sponsor, IRB) will you report the occurrence: IRB.

All serious adverse events (SAEs) will be reported to KCI Inc. within 24 hours of learning of the event. SAEs will be reported for the entire duration of the study protocol, up to 37 days post operation.

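### Section 5f ties the 30-day assessment to not having had an SSI, while the brief summary and schedule give it to everyone, so late SAE ascertainment could depend on the primary outcome

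*Combined protocol and SAP*

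**What the plan says.** The relevant statements in the combined protocol and SAP are these.

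- **Section 5f, text:** the 30-day (±7) outpatient assessment "post-operatively will be included for all patients who did not develop a SSI". Nothing is said about this assessment for patients who did develop one.
- **Brief Summary:** "Subjects will then be seen once at a 30 day" follow-up visit, with no condition on SSI status.
- **Section 5f, schedule of events:** the column "Final Visit 23 to 37 days post op" is marked for SSI assessment, AE monitoring and concomitant medications. The only footnote concerns 24-hour timing.
- **Section 5f, earlier sentence:** "each patient will be followed for up to 37 days and monitored for the development of an SSI and secondary outcomes". Section 5d likewise says that subjects "will then be followed for up to 37 days after the surgery".
- **Section 5e:** the secondary outcomes are "Length of hospital stay and serious adverse events".
- **Section 5i, under the principal monitor heading:** "SAEs will be reported for the entire duration of the study protocol, up to 37 days post operation", and each SAE goes to the device company within 24 hours of the team learning of it.
- **Section 3:** "The follow-up visits will take place at either the Mount Sinai Medical Center or at Mount Sinai-affiliated off-site practices". Section 4 describes follow-up visits as standard of care.

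**The concern.** The 5f sentence does not contain the word only, but if every patient has the visit, the restriction to SSI-free patients has little purpose. A coordinator could reasonably read it as permission to skip the visit once an SSI is recorded, because the primary outcome is then settled.

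Safety is part of the research question in Section 1, and SAEs are a named secondary outcome. The final visit is the only scheduled study contact after Day 5. Under the 5f wording, whether a patient gets it depends on something that happens after randomisation and is expected to happen twice as often in one arm. Late SAEs could then be looked for with different intensity in the two arms.

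**Working it through.** **1. Passages side by side.** Two places give the visit to all subjects (Brief Summary, schedule). One sentence gives it to SSI-free patients (5f text). Three statements cover every patient to day 37 (5d, 5f, 5i), but they set a period and a reporting duty. None says how a late SAE would be found in a patient who has no final visit. No order of precedence between text and table is stated.

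**2. Patients affected.** Inputs from Section 5c: control SSI rate 25%, a 50% reduction giving 12.5% on NPWT, 220 controls and 110 NPWT patients.

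- Every SSI diagnosed before the visit: 0.25 × 220 = 55 controls and 0.125 × 110 = 13.75 NPWT patients, total 68.75, or 21% of 330.
- Half diagnosed before the visit: 27.5 and 6.875, total 34.4.

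**3. Bias in the late-SAE risk difference.** Let r and rn be the late-SAE risks with and without SSI, and ms and mn the shares of those SAEs missed. With p the SSI rate in the arm,

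observed rate = (1 − p) × rn × (1 − mn) + p × r × (1 − ms).

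Subtracting the true rates and then control from NPWT,

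bias (NPWT − control) = (0.25 − 0.125) × (r × ms − rn × mn) = 0.125 × (r × ms − rn × mn).

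Write ms = f × (1 − c), where f is the share of SSIs diagnosed before the visit and c the share of those patients' late SAEs found by other routes. SE = √[oC(1 − oC)/220 + oN(1 − oN)/110], with oC and oN the observed rates.

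The documents give none of r, rn, f, c or mn. All are assumed here, with rn = 10%. Taking f = 50% and c = 50 to 80% gives ms = 10 to 25%.

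| r | ms | mn | Observed control | Observed NPWT | Bias (points) | SE (points) | Bias/SE |
|---|---|---|---|---|---|---|---|
| 10% | 10% | 0 | 9.75% | 9.88% | +0.13 | 3.48 | 0.04 |
| 10% | 25% | 0 | 9.38% | 9.69% | +0.31 | 3.44 | 0.09 |
| 30% | 10% | 0 | 14.25% | 12.13% | +0.38 | 3.90 | 0.10 |
| 30% | 25% | 0 | 13.13% | 11.56% | +0.94 | 3.81 | 0.25 |
| 30% | 25% | 10% | 12.38% | 10.69% | +0.81 | 3.69 | 0.22 |
| 10% | 10% | 10% | 9.00% | 9.00% | 0 | 3.34 | 0 |
| 10% | 10% | 20% | 8.25% | 8.13% | −0.13 | 3.20 | −0.04 |
| 10% | 0 | 20% | 8.50% | 8.25% | −0.25 | 3.23 | −0.08 |

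True rates are 10% in both arms when r = 10%, and 15.0% control against 12.5% NPWT when r = 30%. The sign turns where rn × mn = r × ms.

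**4. Sensitivity to f.** If every SSI is diagnosed before the visit (f = 100%, the basis of the 55 and 14 above), ms doubles to 20 to 50%. With mn = 0 the bias then doubles to between 0.125 × 0.10 × 0.20 = +0.25 and 0.125 × 0.30 × 0.50 = +1.88 points. The latter is 0.52 of its SE of 3.63.

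**The case against.** The strongest reply is that one loosely worded sentence stands against several unconditional statements. The sentence excludes nobody. It may only be meant to secure a wound check in patients whose primary outcome is still open. The schedule, which is the most operational text, sets no condition. The 24-hour SAE duty in Section 5i is triggered by the event and not by a visit, and Section 4 says that most data come from standard-of-care records and visits. SSI patients may well be seen more often than others. The numerical range reflects assumed inputs and shows no material bias.

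Much of this stands. The restrictive reading is an inference, loss of late SAEs is a risk and not a certainty, and neither the size nor the direction of the bias is known. It does not remove the conflict. A duty to report an SAE after learning of it is not a procedure for learning of it, and no such procedure is written for an SSI patient without a final visit. If the schedule is the intent, the 5f sentence is wrong. If 5f is the intent, the Brief Summary and schedule are wrong and late safety follow-up of SSI patients is unspecified. In either case text has to change.

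**Conclusion.** The concern holds, as a minor one. The textual conflict is certain. The consequence is a possible difference between arms in how late SAEs are found. The bias acts against NPWT if late SAEs are found less completely in SSI patients than in SSI-free patients, and is negligible or reverses if SSI patients have more routine contact. Over the scenarios with half of SSIs diagnosed before the visit, it stays within a quarter of a standard error. It reaches about half of one only if all SSIs are diagnosed first, late-SAE risk after SSI is 30%, half of those patients' late SAEs are missed, and none are missed in SSI-free patients. Every late-SAE risk and capture share is an assumption. If SAEs are analysed as patients with at least one event, the effect is smaller, because patients with an earlier SAE are already counted. The binary SSI outcome is untouched: patients who would skip the visit already count as events.

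**What to change.** Reconcile Section 5f with the Brief Summary and the schedule. One sentence suffices: the day 23 to 37 assessment is done for all randomised patients, whether or not an SSI has developed, and SAEs are collected to the same end date in both arms. Section 5i already sets 37 days without distinction by arm, so the second clause mainly confirms that an SSI does not end collection early.

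The visit is already planned for everyone in two places. The added work, compared with the literal 5f wording, is data collection at that visit for at most about 69 patients (55 + 13.75), or about 34 if half of SSIs are diagnosed before it.
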